4.1 Description of Trial Design

- **Description of Intervention Model**

- This randomized control trial features two parallel groups: an active comparator (control) group and a treatment group, aiming for a total of 146 participants diagnosed with one of the following cancers - Breast, Colorectal, Prostate Lung and Other Cancer.

- The treatment group will be given live coactive coaching and personalized digital application program focused on Exercise and Meditation, supplemented with evidence-based facts on Diet, Sleep, and other lifestyle practices
- On the other hand, the control group will be given a digital application with expert guidelines on lifestyle modification, available publicly but with no live coaching and personalization.
- In essence, this is a superiority trial aimed at establishing that CT's program is more effective in improving outcomes.

- **Description of Trial Duration**

- The overall duration for an individual participant is anticipated to be 48 weeks (minimum 3, up to 5 days per week, 45 mins each session) for the active phase, with a 6 month follow-up period for long-term data collection.
- This duration allows for a comprehensive assessment of the intervention's immediate and sustained impacts on health outcomes and healthcare costs.

- **Method of Assignment to Trial Intervention**

- Participants in each group will be recruited transparently through online advertisements while ensuring balanced representation across cancer types.
- Blinding: The participants will not be aware if they are in control or test group.
- Number of Arms: Two – one control and one treatment group.

4.2 Rationale for Trial Design

- **Rationale for intervention model**

- The chosen randomized control trial (RCT) model with an active comparator allows for a direct and meaningful comparison between Complement Theory's live coactive guidance with a physical coach and personalized program and the standard guidance available to cancer survivors. This

model is particularly suited to our objectives as it accommodates the evaluation of a complex intervention involving live coactive coaching and digital support, unlike traditional drug trials. This approach ensures that any observed differences in outcomes can be attributed with greater certainty to the unique components of the Complement Theory program, thereby providing a clear assessment of its added value over standard care practices.

- **Rationale for duration**

- The trial duration has been carefully selected to ensure sufficient time to observe meaningful changes in Quality of Life, Presenteeism and Absenteeism. A 12-month intervention period, followed by a 6 month-long follow-up, allows us to capture both the immediate and sustained impacts of lifestyle modifications on health outcomes. As an exploratory effort, the extended follow-up period enhances our ability to monitor long-term effects, particularly relevant for outcomes like cancer recurrence and cancer progression in three cancer types (prostate, lung and colorectal). The durations for these exploratory metrics in Breast cancer are much longer and hence not considered.

- **Rationale for Endpoints**

- The trial endpoints have been selected for their clinical relevance and their capacity to provide reliable and valid measurements of the intervention's effect. Quality of Life provides a patient-centered measure that is both prognostically important and assessable in the short term. Both the control and treatment groups are offered exercise oncology guidance, however our hypothesis is that CT's live coactive coaching is expected to have better Quality of Life measured through the FACT-G questionnaire. FACT-G also helps us measure the impact on Pain, Fatigue and Sleep Quality, providing a comprehensive assessment of well-being among cancer survivors. Lastly, measures of employee absenteeism and

presenteeism are particularly relevant to both employers and employees, providing insight into the program's potential to improve work-related outcomes in addition to health parameters.

- **Rationale for Comparator**

- The control group's engagement with a digital application with publicly available expert guidelines on lifestyle modification represents current non-pharmacological supportive care options available to cancer survivors.
- This comparator was selected to underscore the added value and distinct benefits of Complement Theory's personalized and interactive wellness approach against more generic and self-guided lifestyle resources.

4.3 Access to Trial Intervention After End of Trial

- Post-trial, participants will have the opportunity to continue accessing the Complement Theory's program Free of Cost. Details on extended access will be communicated towards the trial's conclusion.

4.4 Start of Trial and End of Trial

- Start of Trial: Defined by the first participant's enrollment (FPI).
- End of Trial: Marked by the last scheduled follow-up of the final participant, with an anticipated end date eighteen months post final participant enrollment to allow comprehensive long-term outcome analysis.
- Early Termination: Criteria for early trial termination will include lack of efficacy, safety concerns, or regulatory guidance, detailed in Section 10.5 with responsibilities clearly outlined for both sponsor and investigator.

Section 5: TRIAL POPULATION

5.1 Selection of Trial Population

- Participants for this trial will be identified through targeted online advertisements on platforms such as Facebook and Google. This approach ensures an unbiased recruitment process, enhancing our chances of assembling a representative

sample of the U.S. cancer survivor population. Consequently, we do not intend to impose specific gender or race quotas.

5.2 Rationale for Trial Population

- We have specifically chosen cancer survivors aged 21 yrs and above who have received cancer treatment (ie either surgery, chemotherapy, radiation, or immunotherapy) within the past six months. This demographic is selected based on evidence suggesting they stand to significantly benefit from our intervention in terms of improved health outcomes, aligning with employer interests.

5.3 Inclusion Criteria

- Cancer Type : Breast, Prostate, Colorectal, Lung and Other Cancers
 - Other Cancers here refers all other cancer types apart from Breast, Prostate, Colorectal and Lung Cancer
- Cancer Stage: Stage 1 to 4
- Treatment Status: Has undergone any cancer-related treatment in last 12 months
- Age : 21 yrs and above
- Permission to access to last 1 year digital health records
- Access to smartphone or a tablet

5.4 Exclusion Criteria

- Excludes individuals who have undergone surgery within the last 4 weeks or will undergo surgery in the next 4 weeks
- Participants declared medically unfit by their physicians to do physical exercise
- ECOG Score 3, 4 or 5

5.5 Lifestyle Considerations

- No lifestyle restrictions during the trial

5.6 Screen Failures

- Documentation: All screen failures will be documented, including the specific reason(s) for the failure. This information is crucial for trial records and may inform future trial design adjustments or participant recruitment strategies.
- Immediate Notification: Participants who do not meet the eligibility criteria at screening will be promptly informed of their screen failure status. The participant can also get detailed explanation regarding the specific criteria not met by writing to trial support team (mentioned on the landing page).
- Rescreening may be considered under the following conditions:
 - Reversible Conditions: If the screen failure is due to a reversible condition or temporary circumstance that rendered the participant ineligible (e.g., recent surgery), rescreening may be acceptable once the condition has resolved.
 - Updated Information: If new medical information becomes available that could change the initial screening outcome (e.g., updated diagnostic tests, revised cancer staging), rescreening is permissible.
 - All such participants would be able to write to trial support team to get rescreened.

Section 6: TRIAL INTERVENTION AND CONCOMITANT THERAPY

6.1 Schedule of Events

Schedule of events for test/treatment group:

Intervention or Assessment (Test)	Baseline (Day -30 to -1)	Week	Week	Month 1-6 (Every 30 days)	Month 7-18 (Every 30 days)
		1/3/5/7/9/11/13/15/17/19/21/23/...	2/4/6/8/10/12/14/16/18/20/22/24/...		
Live Coactive Lifestyle Coaching		X	X		

- 3-5 days per week, 45 mins each					
Async access to Lifestyle modification content curated by CT		X	X		
Informed Consent	X				
Eligibility Criteria Assessment	X				
Demographic Details	X				
EHR Access Consent	X				
Claims Data Access	X		X		X
QoLS (FACT-G Form)	X		X		X
Weight	X		X		X
Motivation to work	X	X			X
Employee Performance Review	X	X			X
Absenteeism Questions	X	X			X
Claim data validation with				X	X

survivor						
Cancer Progression Status					X	X

Schedule of events for active comparator (control) group:

Intervention or Assessment (Test)	Baseline (Day -30 to -1)	Week	Week	Month 1-6 (Every 30 days)	Month 7-18 (Every 30 days)
		1/3/5/7/9/11/13/15/17/19/21/23/... /47	2/4/6/8/10/12/14/16/18/20/22/24/... /48		
Async access to publically available lifestyle modification guidance		X	X		
Informed Consent	X				
Eligibility Criteria Assessment	X				
Demographic Details	X				
EHR Access Consent	X		X		X
Claims Data Access	X		X		X
QoLS (FACT-G Form)	X		X		X
Weight	X		X		X
Motivation to work	X	X			X
Employee Performance Review	X	X			X
Absenteeism Questions	X	X			X
Claim data validation with survivor				X	X
Cancer Progression Status				X	X

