7.3 Lost to Follow-Up

1. We will provide clear communication about the importance of follow-up visits with some incentives for participation and maintaining regular contact with participants through phone calls, emails or reminders.
2. Offer flexibility in scheduling
3. Follow up duration will be 4 weeks after a lack of response. We will re-attempt to contact the survivor after a brief 2 week pause after which we will no longer contact the survivor.

Section 8: TRIAL ASSESSMENTS AND PROCEDURES

This section outlines the comprehensive assessments and procedures deployed throughout the trial to ensure accurate, reliable data collection across all specified endpoints, emphasizing adherence to the trial's design and objectives.

Data Collection and Assessment Methods

- Claims Record: To accurately assess the financial impact of the intervention on healthcare expenditures, participants will be requested to provide Claims Records and Explanation of Benefits documentation. This comprehensive data set will encompass costs related to hospitalization, medication, lab visits, and other relevant medical expenses.
- Electronic Health Records (EHR): For a detailed and objective view of medical histories, participants will be asked to access their Electronic Health Records through platforms like MyChart. This step aims to enrich the claims data with additional medical record insights with information like days of hospitalization, disease for which treatment was undertaken, whether it was an Emergency visit or not and so on.
- Patient-Reported Outcomes: In a complementary approach to objective data collection, participants will also self-report on various aspects including healthcare

expenditures, quality of life (measured by FACT-G) and cancer progression status. Furthermore, they will report on absenteeism (detailing the number of leave days taken, including short-term or long-term disability status) and presenteeism (evaluated through work motivation and performance review scores). These self-reported metrics will be securely collected through a digital platform, aiming to supplement and validate the analysis of claims and EHR data.

Live Coaching Consistency

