8.2 Efficacy Assessments and Procedures

Healthcare Expenditure Reduction (Trial Objective 1):

- Endpoint: Total healthcare expenditure, including hospitalization costs, medication expenses, outpatient visits, etc.
- Assessment Procedure: Conduct comprehensive assessments of healthcare expenditure for participants in both the intervention and control groups at specified time points (e.g., baseline, 3 months, 6 months, 12 months and 18 months).
- Data Collection: Obtain detailed data on healthcare utilization, costs of medical services, medication expenses, and related healthcare expenditures through EHR access granted by participants, and participant-reported information.
- Analysis: Calculate the mean total healthcare expenditure for each group and compare the differences between the intervention and control groups over the trial period.

Impact on Adherence to Treatment (Trial Objective 2):

- Endpoints: Change in MMAS-8 scores
- Assessment Procedures: Administer the MMAS-8 questionnaire to assess adherence levels to treatment regimen at baseline and specified time points during and after the intervention period.
- Data Collection: Obtain self-reported scores from participants on adherence levels.
- Analysis: Calculate the mean difference in change in survey scores between the intervention and control groups at each time point to evaluate the impact

Improvement in Quality of Life Score (QoLS), Pain, Sleep and physical activity (Trial Objective 3):

- Endpoint: Change in FACT-G, GLTEQ, BPI-ShortForm, PROMIS scores measuring quality of life, physical activity, pain levels, and sleep
- Assessment Procedures: Administer the above four questionnaires to assess participants' at baseline and specified time points during and after the intervention period.
- Data Collection: Obtain self-reported scores from participants on Quality of Life, Pain levels, and behavior change specifically with Healthy Diet intake and ability to do physical activity.
- Analysis: Calculate the mean difference in change in scores between the intervention and control groups at each time point to evaluate the impact of the intervention.

Reduction in Employee Absenteeism (Trial Objective 4):

- Endpoint: Number of leave days taken by employed cancer survivors due to health issues.
- Assessment Procedures: Track the number of leave days (sick leave, short-term disability, long-term disability) taken by participants in both groups throughout the trial period.

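### The EHR Access Consent row in 6.1 differs by arm without explanation; if followed as written, it allows fuller EHR capture in controls than in the test arm

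*Protocol*

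**What the plan says.** Section 6.1 of each document has one schedule table per arm. In the Protocol the test-group row reads "EHR Access Consent X", with a single mark at baseline. The control-group row reads "EHR Access Consent X X X", with marks at baseline, in the even-week column ("2/4/6/8/10/12/14/16/18/20/22/24/... /48") and in the late column ("Month 7-18 (Every 30 days"). The Combined protocol and SAP shows the same difference, with even weeks ending at 24. No other row schedules EHR contact in either arm.

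The claims row, "Claims Data Access X X X", is the same in both arms. FACT-G, weight, the work questions, claims validation and cancer progression status are also scheduled alike.

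Section 8 (Data Collection and Assessment Methods) gives claims as the cost source: "participants will be requested to provide Claims Records and Explanation of Benefits documentation". The EHR is there to enrich the claims with "days of hospitalization, disease for which treatment was undertaken, whether it was an Emergency visit or not and so on". Section 8.2 of the Combined document, under the expenditure objective, says the data are obtained "through EHR access granted by participants, and participant-reported information", and that line does not mention claims.

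**The concern.** EHR records feed outcomes in this trial, and they arrive only when participants act. Section 8 has participants asked to open their own records, and 11.2 has them share the data. Whether and when a person is asked can therefore affect what is received. If staff prompt controls every two weeks and then monthly, but prompt test participants once before treatment starts, an admission or emergency visit recorded only in the EHR is more likely to reach the database for a control.

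This error would run in the direction of the hypothesis, because missed cost in the test arm looks like a saving. Randomisation and intention-to-treat analysis do not correct it. Imputation does not either, because an event that was never retrieved is not flagged as missing.

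**Working it through.** **Count of marks per participant**

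- Protocol, control: 1 baseline + 24 even weeks (2 to 48) + 12 monthly points (7 to 18) = 37. Week 30 and month 7 both fall on day 210 (30 × 7 = 7 × 30), so there are 36 distinct days; hence up to 37.
- Combined document, control: 1 + 12 even weeks (2 to 24) + 12 = 25.
- Test arm, both documents: 1.

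**The plan's own sample size for expenditure**

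Inputs from 9.7 of both documents: means 10000 and 8000, a stated variance of 4000, one-sided alpha 0.05, power 80%, 1:1 allocation, 102 in total.

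- Normal approximation with 4000 as a standard deviation: n per arm = 2 × (1.645 + 0.842)² × (4000/2000)² = 49.5, so 50.
- One-sided t-test: 51 per arm, power 80.6%. This reproduces 102.
- Taken literally as a variance, 4000 would give 1 per arm, so the figure must be a standard deviation.
- With 30% drop-out: 102/0.7 = 145.7, so 146, as stated.

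**What differential capture could do**

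The documents give neither the share of cost found only in the EHR nor any loss of capture. Both are assumed below. Take no true effect, a mean of 10000 in both arms, SD 4000 and 51 per arm.

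- False saving = 10000 × EHR-only share × fraction of that share missed in the test arm.
- Standard error of the difference = 4000 × √(2/51) = 792.
- False-positive rate = 1 − Φ(1.645 − false saving/792).

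Example: a 25% share with 20% missed gives 10000 × 0.25 × 0.20 = 500. Then 500/792 = 0.63, and 1 − Φ(1.01) is about 15.5%.

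| Assumed EHR-only share | False saving at 5-20% missed | False-positive rate |
|---|---|---|
| 0% | 0 | 5% |
| 10% | 50-200 | 5.7-8.2% |
| 25% | 125-500 | 6.9-15.5% |

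**Which endpoints are exposed**

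- Combined document: total expenditure, the primary endpoint, because 8.2 names EHR access as a source.
- Protocol: total expenditure, which is exploratory, together with the hospital-day and emergency detail that the EHR adds.
- Not exposed: FACT-G (the Protocol's primary endpoint), the work outcomes and self-reported progression status. All are collected alike in both arms.

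**The case against.** The strongest reply is that the row is labelled as consent, not retrieval. One baseline consent could cover the whole trial, so a reader who infers 37 data pulls against 1, or that controls are in fact captured more fully, goes beyond the documents. This stands: the counts are scheduled marks only.

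A copied row is also a plausible explanation, because the control marks are the same as those of the claims row. No text supports a deliberate difference in procedure. This stands too.

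There are safeguards common to both arms. Claims access and claims validation follow one schedule, Section 8 treats claims as the comprehensive cost source, expenditure is also self-reported, and 11.2 recommends 6 to 18 months of access without regard to arm. These lower the risk but do not remove it. The access period is only a recommendation, and if access lapses after month 6, only controls have a scheduled renewal. The entry permission covers the year before enrolment, not the follow-up.

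A reader might also infer a large inflation. If 5%, 10% or 20% of all cost were missed in the test arm, the rate would be 15.5%, 35.1% or 81.1%. Those figures assume in effect that all cost depends on the EHR (or an equivalent loss) and leave out zero. With claims collected alike in both arms, the documents give no basis for them. Nor do they support bias in cancer progression, since Section 8 lists progression status as self-reported.

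**Conclusion.** The arm difference in the EHR row is real, appears in both documents and is unexplained. Whether it is a drafting error or an intended procedure cannot be settled from the text. Followed as written, it allows arm-dependent ascertainment in favour of the intervention, because no other row schedules EHR contact and the records depend on participants supplying them.

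It matters most for the Combined document, where it touches the primary endpoint. In the Protocol it reaches exploratory expenditure only. The size is unknown: no inflation above 5% if nothing depends on the EHR alone, and up to 8.2% or 15.5% under the assumed 10% or 25% shares with at most 20% missed. These rates illustrate the mechanism and are not estimates for this trial. The documents do not show that capture actually differs between arms.

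**What to change.** Make the EHR row identical in the two 6.1 tables of each document. Keep consent separate from retrieval: consent at baseline in both arms, and one EHR retrieval schedule and look-back period for both arms, placed on the claims-access time points they already share. State that EHR-based endpoints are derived only from retrievals scheduled in both arms. If the difference was intended, the sponsor should say why and how expenditure is protected from it.

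The cost is an edit to one row and a short statement on retrieval, plus a few more EHR requests in the test arm or fewer in control. The sample size stays at 102 evaluable and 146 randomised.

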6.2 Rationale for Trial Intervention

Previous studies have shown that exercise at recommended levels can lead to 35-45%^{5,6} recurrence reduction among cancer patients, and 40-50% cancer mortality reduction^{5,6}. Patients report improvements in physical function, symptom management, and quality of life without significant adverse effects. Meditation has shown to reduce depression and increase in NK cells production⁷. However, less than 15%³ of cancer patients practice clinically recommended regimen. We hypothesize that Live coactive instructions that are personalized will increase the adherence to exercise and related lifestyle modifications such as meditation & nutrition, and will enable the benefits outlined above.

6.3 Dosing and Administration

Details for Trial Intervention (Test Group):

- Timing of Intervention: Participants can log in at their convenience, with the flexibility to schedule exercise coaching sessions according to their preferences and availability.
- Intervention Structure: Over the course of 12-months or 48 weeks, each participant will participate in 3-5 weekly live sessions. Each session, spanning approximately 45 minutes, combines 30 minutes of targeted exercise with 7 minutes of meditation. Each session will be supervised live by a coactive coach for each participant. The program is strategically developed to progressively escalate in intensity:
 - Each session will consist of an optimal combination of Aerobic and Strength exercises.
 - Flexibility and Balance exercises will be included as supplemental exercises in the sessions.

12 Months Program Structure

Months 1 and 2

- Initially participants will be given 1:1 coaching to ensure that the participants get immediate feedback as well as modifications as needed.
- 10 workouts will be presented to the participants in Month 1 and 2. Each workout will be repeated 4 times, hence completing 40 days of workouts.
- The first 2 weeks will be “Light”: allowing the participants to complete the 10 workouts in flow while building confidence without pushing too hard or feeling too sore.
- The second 2 weeks will be “Light/Moderate”: allowing the participant to repeat the same 10 workouts, feel more confident in their ability to finish each workout because they are not brand new, but also experience a slight challenge on the body with the order in which the workouts are laid out.
- The third 2 weeks will be “Moderate”: the participants are expected to begin to feel stronger and more capable at this point which allows them to push a little harder and enjoy the challenge without burnout.
- The fourth 2 weeks will be “Moderate/Hard”: the participant by now should be experiencing what it’s like for the body to master the foundational goals above.

Month 3, 4, 5 and 6

- Next set of 10 workouts will be introduced in months 3 and 4, and likewise in months 5 and 6.

Month 6 to 12

- Based on their ability and progress, participants will be slowly graduated from 1:1 coactive sessions to Group-coactive sessions.

- Planned Route of Administration: The intervention will be administered remotely via the online platform, accessible through mobile devices.
- Specific Instructions: Participants will receive login credentials and instructions for accessing the software upon enrollment in the trial. They will be guided through the process of scheduling and participating in live exercise sessions, including how to navigate the platform and interact with their exercise coach.
- Delayed or Missed Intervention: Participants who miss scheduled exercise coaching sessions will have the opportunity to reschedule or make up missed sessions at a later time within the 12-month intervention period.
- Coaching Modifications: The coaching strategy includes personalized exercise recommendations tailored to each participant's unique needs and physical condition.
 - For instance, in cases of severe fatigue post-chemotherapy, coaches may adapt the program to include gentle activities like simple stretching followed by soothing meditation to ensure participant comfort and safety.
- Start and Stop Treatment: Participants are encouraged to engage consistently in the software app throughout the 12-month intervention period. However, they have the flexibility to start and stop treatment as needed, with the option to resume participation at their discretion.
- Dose Reductions: As this intervention does not involve pharmaceuticals, there are no dose reductions; however, adjustments to the frequency, intensity and approach of exercises may be made in response to participant feedback and progress (as suggested above with examples).

Details for Control Product:

- Timing of Intervention: Participants can log in to the app at their convenience to learn about exercise, diet and meditation guidelines.

- Duration: Participants will have access to the Active Comparator for the same 12-month period as the intervention arm.
- Planned Route of Administration: The Active Comparator will be administered remotely via the online platform, mirroring the administration method of the experimental intervention.
- Specific Instructions: Participants will receive login credentials and instructions for accessing the software upon enrollment in the trial.
- Delayed or Missed Doses: Participants in the control arm are free to manage how they like to use the app within the 12-month intervention period.
- Dose Modifications: N/A
- Start and Stop Treatment: Participants in the control arm have the same flexibility to start and stop treatment as those in the intervention arm, with the option to resume participation at their discretion.
- Dose Reductions: N/A

Trial Intervention Dose Modification

- For the intervention provided in this trial, the intervention involves personalized exercise coaching sessions tailored to each participant's needs and capabilities.
- The intensity and frequency of exercise sessions will be adjusted dynamically based on individual responses (such as RPE score), progress, and tolerance, as guided by the exercise coach. Therefore, there are no predefined criteria for dose modification or dose titration.

